6.5.2. Antiseptic Therapy

Participants are required to use a daily antiseptic wash on their HS lesions. Allowable antiseptic washes are limited to one of the following: soap and water, a topical antiseptic wash containing chlorhexidine gluconate, triclosan, or benzoyl peroxide, or a dilute bleach bath.

6.5.3. Wound Care

Concomitant use of wound care dressings on HS wounds is allowed; however, options are limited to alginates, hydrocolloids, and hydrogels.

6.5.4. Analgesic Therapy

Use of opioid analgesics is prohibited for 14 days prior to the baseline visit regardless of HS or non-HS reasons. During the study, concomitant use of opioid analgesics is also prohibited, with the exception of tramadol as detailed below.

Oral analgesics for HS-related pain are prohibited 14 days prior to the baseline visit. If a participant is on a stable dose of a non-opioid analgesic (PRN is not considered stable) for a non-HS medical condition (eg, osteoarthritis), the participant may continue the analgesic, provided the dose is stable for 14 days prior to baseline and is anticipated to remain stable throughout study participation.

If a participant's pain (HS-related or non-HS-related) worsens after baseline, they may initiate analgesic therapy at any time as follows:

For HS-related pain, permitted analgesics are limited to:

- Ibuprofen (at a dose of up to 800 mg by mouth every 6 hours) not to exceed 3.2 grams/24 hours; AND/OR
- Acetaminophen as per local labeling; AND/OR
- If HS-related pain is uncontrolled with ibuprofen and/or acetaminophen at the above dosing regimens after the baseline visit, participants can be prescribed tramadol (at a dose of up to 100 mg by mouth every 4 hours), not to exceed 400 mg/24 hours.

Dose adjustments of ibuprofen, acetaminophen, or tramadol, and use of these analgesics on an "as needed" (PRN) basis for HS-related pain up to the maximum permitted dose and frequency, are allowed during the study.

From Screening through Week 40, participants will not be permitted to use any analgesics related to HS pain within 24 hours of a scheduled study visit. All analgesics and dose adjustments will be captured in the source and on the appropriate eCRF.

For non-HS-related pain:

• All other non-opioid analgesics and tramadol are allowed at the recommended or prescribed dose.

6.5.5. Prohibited Therapy

Participants who initiate the following treatments during study participation must have their study intervention discontinued:

- Phototherapy (PUVA and/or UVB)
- All biologic therapy with a potential therapeutic impact on the disease being studied, including but not limited to the following:
 - Adalimumab (Humira®)
 - Anakinra (Kineret®)

- Abatacept (Orencia®)
- Natalizumab (Tysabri®)
- Ustekinumab (STELARA)
- Etanercept (Enbrel®)
- Infliximab (REMICADE®)
- Rituximab (Rituxan®)
- Tocilizumab (Actemra®)
- Efalizumab (Raptiva®)
- Golimumab (SIMPONI®)
- Certolizumab (Cimzia®)
- Belimumab (Benlysta®)
- Secukinumab (Cosentyx®)
- Ixekizumab (Taltz®)
- Brodalumab (Siliq®)
- Tildrakizumab (Ilumya®)
- Any investigational agents for the treatment of HS.
- Any other systemic drug therapies for HS, including but not limited to MTX, cyclosporine, and retinoids.
- Concomitant use of oral antibiotic therapy for HS or inflammatory disorders. Systemic antibiotic use (including oral) is allowed for the treatment of acute infections such as bacterial, viral, or fungal.
- Oral or injectable corticosteroids for the treatment of HS, except for protocol allowed intralesional rescue therapy as outlined in Section 6.5.1.
- Surgical or laser intervention for an HS lesion except as outlined in Section 6.5.1, Rescue Therapy.

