7.1. Discontinuation of Study Intervention

A participant's study intervention must be discontinued if any of the following occur:

- The investigator believes that for safety reasons or tolerability reasons (eg, AE) it is in the best interest of the participant to discontinue study intervention.
- The participant has a serious adverse reaction that is temporally related to an injection or an infusion including an injection-site or infusion reaction, resulting in bronchospasm with wheezing and/or dyspnea that requires ventilatory support OR that results in symptomatic hypotension with a decrease in systolic blood pressure >40 mm Hg or blood pressure <90/60 mm Hg. This may include events of National Cancer Institute Common Terminology Criteria for Adverse Events (NCI-CTCAE) toxicity grade ≥3. In general, discontinuation of study intervention administration must be considered for participants who develop a severe injection-site or infusion reaction.
- The participant or their legally acceptable representative withdraws consent/assent for administration of study intervention.
- The participant becomes pregnant or plans a pregnancy during the study period. Refer to Appendix 7 (Section 10.7), Contraceptive and Barrier Guidance and Collection of Pregnancy Information.
- The initiation of protocol-prohibited medications, treatments, or interventions (outlined in Section 6.5, Concomitant Therapy) that have an impact on HS efficacy evaluations.
- The participant has a malignancy including squamous cell skin cancer. Consideration may be given to allow participants, who develop ≤2 basal cell skin cancers and who are adequately treated with no evidence of residual disease, to continue to receive study intervention.
- A systemic opportunistic infection.
- A recurrent or chronic serious infection.
- The participant is deemed ineligible according to the following TB screening criteria:
 - A diagnosis of active TB is made.
 - A participant has symptoms suggestive of active TB based on follow-up assessment questions and/or physical examination or has had recent close contact with a person with active TB and cannot or will not undergo additional evaluation.

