2.4.1.2. Per Protocol Analysis Set

The primary endpoint will also be analyzed using the per-protocol population, which includes participants who are generally compliant with the protocol.

Specifically, the per protocol population includes participants in FAS except those

- who did not meet the inclusion criteria 6 in the protocol as listed below:
 - Have a total abscess and inflammatory nodule (AN) count of ≥ 3 at the screening and baseline.
- who met the exclusion criteria 2 in the protocol as listed below:
 - Has a draining fistula count of >20 at the baseline visit.
- who did not complete the specified exposure to study agent as outline below
 - participants randomized to placebo at Week 0 who received guselkumab prior to Week 16.
 - participants randomized to guselkumab 1200 mg at Week 0 but did not receive all scheduled guselkumab administrations prior to Week 16.
 - participants randomized to guselkumab 200 mg at Week 0 but did not receive all scheduled guselkumab administrations prior to Week 16.

However, for those who did not complete the specified exposure to study agent as outline above, participants who discontinued the study agent due to unsatisfactory therapeutic effect (lack of efficacy) or an adverse event (AE) of worsening of HS, or participants who started prohibited medications and continued receiving study agents prior to the specified timepoint for the endpoints will be included in the per protocol analysis and the treatment failure rules specified in Section 5.2.3.2 will apply.

Participants who were excluded from the per protocol analyses will also be summarized.

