5.2.3.1. Treatment Failure Criteria

Participants who discontinue study intervention due to lack of efficacy or an AE of worsening of HS, or who started a protocol-prohibited medication or therapy during the study that could improve HS, are considered treatment failures.

The particular protocol-prohibited medications/therapies include:

Systemic Therapies:

- Any immunodulatory biologic therapy
- Any conventional systemic immunosuppressive therapy
- Any systemic corticosteroid for HS
- Any systemic antibiotic therapy for HS or any indications other than infection
- Any systemic retinoid

- Investigational Agents for HS
- Analgesic therapy for HS (Section 5.2.3.2.1)
- Phototherapy (PUVA and/or UVB) for any indications and other phototherapies for indication of HS

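### The per-protocol set can lose guselkumab participants stopped for prohibited HS therapy while keeping the same participants on placebo as HiSCR failures

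*Protocol*

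**What the plan says.** **Stopping rule.** Protocol 6.5.5 introduces its list of prohibited therapies with: "Participants who initiate the following treatments during study participation must have their study intervention discontinued". Protocol 7.1 repeats this among the conditions that require discontinuation: "The initiation of protocol-prohibited medications, treatments, or interventions (outlined in Section 6.5, Concomitant Therapy) that have an impact on HS efficacy evaluations".

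**Failure rule.** SAP 5.2.3.1 classes as failures participants who stop for lack of efficacy or an AE of worsening HS. Separately, it covers those "who started a protocol-prohibited medication or therapy during the study that could improve HS, are considered treatment failures". SAP 5.2.3.2 dates failure from the earlier of the two events.

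**Per-protocol exclusions for exposure (SAP 2.4.1.2).**
- 1200 mg IV arm: "participants randomized to guselkumab 1200 mg at Week 0 but did not receive all scheduled guselkumab administrations prior to Week 16".
- 200 mg SC arm: "participants randomized to guselkumab 200 mg at Week 0 but did not receive all scheduled guselkumab administrations prior to Week 16".
- Placebo arm: only "participants randomized to placebo at Week 0 who received guselkumab prior to Week 16".

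**Per-protocol exception (same section).** Two groups are restored, and the failure rules then apply to them:
- "participants who discontinued the study agent due to unsatisfactory therapeutic effect (lack of efficacy) or an adverse event (AE) of worsening of HS"
- "participants who started prohibited medications and continued receiving study agents prior to the specified timepoint for the endpoints will be included"

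SAP 5.3.6 repeats the primary HiSCR analysis on this set.

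**The concern.** The exception appears intended to keep treatment failures in the per-protocol set as failures, because it sends them to the rules in 5.2.3.2. Its second branch is tied to continued dosing, whereas protocol 6.5.5 and 7.1 call for dosing to stop. A guselkumab participant who is handled as those sections direct can therefore miss both branches.

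Such a participant is a non-responder in the FAS but disappears from the denominator of the guselkumab per-protocol rate. Placebo participants are not excluded for missed doses, so the same course of events on placebo stays in as a failure. Membership also comes to depend on which stop reason the site records. Two participants with the same clinical course could be treated differently.

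What is at stake is how far the per-protocol HiSCR result can be read as support for the FAS result.

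**Working it through.** **1. The plan's own figure.** Inputs from protocol 9.2: 60 per arm, 25% against 55%, alpha 0.05 (two-sided per SAP 1.4). Pooled-variance normal approximation:
- standard error under the null = sqrt(2 × 0.40 × 0.60 / 60) = 0.0894
- standard error under the alternative = sqrt((0.25 × 0.75 + 0.55 × 0.45) / 60) = 0.0851
- power = Φ((0.30 − 1.96 × 0.0894) / 0.0851) = 92.9%

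Table 1 states 93%, so it reproduces. The other five rows also agree, to within 1 point. Power refers to the FAS, so the per-protocol definition does not change it.

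**2. Who is in the per-protocol set.** Scheduled guselkumab doses before Week 16 fall at Weeks 0, 4, 8 and 12 in both active arms (protocol 4.1). For a participant who meets the lesion-count conditions and starts a prohibited HS therapy before Week 16:

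| Course | Guselkumab | Placebo |
|---|---|---|
| Stopped before the Week 12 dose; prohibited therapy recorded as reason | **Out** | In, non-responder |
| Stopped before the Week 12 dose; lack of efficacy or worsening HS recorded | In, non-responder | In, non-responder |
| All doses through Week 12 received | In, non-responder (never excluded) | In, non-responder |
| Missed a dose, later doses given | In, non-responder (second branch) | In, non-responder |

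The placebo column assumes no guselkumab before Week 16. In the FAS every cell is a non-responder. Only the first row differs between arms.

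**3. Effect on the rate.** Let k be the number of guselkumab participants in the first row. The documents give no value, so k = 0 to 6 of 60 (0 to 10%) is an assumption. Expected responders are 0.55 × 60 = 33, and the per-protocol rate is 33 / (60 − k). Placebo stays at 15/60 = 25.0%.

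| k | Guselkumab rate | Difference from placebo |
|---|---|---|
| 0 | 33/60 = 55.0% | 30.0 points |
| 1 | 33/59 = 55.9% | 30.9 points |
| 3 | 33/57 = 57.9% | 32.9 points |
| 6 | 33/54 = 61.1% | 36.1 points |

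**4. If there were no true effect.** With 25% response in both arms, k = 3 gives 15/57 − 15/60 = +1.3 points and k = 6 gives 15/54 − 15/60 = +2.8 points. In 400,000 simulated trials (unstratified pooled z-test), the chance of a nominally significant per-protocol result favouring guselkumab was 2.6% with none removed. It was 3.7% with an expected 5% of the guselkumab arm removed, and 5.3% with 10%.

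**The case against.** The literal gap is hard to dispute, but several stronger readings are tempting and the documents do not support them.

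- **A reader might infer that the rule is inverted, keeping violators and deleting compliant participants.** SAP 4.5 lists receipt of a disallowed concomitant treatment as a major deviation, so those dropped are not simply compliant. Leaving out people who deviated and also missed doses is a conventional per-protocol choice. Nor is everyone who continues dosing in breach of 6.5.5. SAP 5.2.3.1 names any systemic retinoid and any conventional systemic immunosuppressant without limiting them to HS, while 6.5.5 covers other systemic drugs given for HS.
- **A reader might infer that every such stop is excluded because 7.1 lists prohibited therapy separately.** Section 7.1 lists conditions for stopping. It is not the eCRF reason list, and it does not name lack of efficacy at all. The eCRF categories are not shown, and some of these stops may be recorded as lack of efficacy or worsening HS and so be kept.
- **A reader might infer that the lean comes from the exception alone.** It depends on the arm-specific dosing rule. With 3 removed from each arm the difference is 33/57 − 15/57 = 31.6 points. With 3 removed from guselkumab and 6 from placebo it is 57.9 − 27.8 = 30.1 points, close to the FAS value of 30.0. A symmetric dosing rule would therefore shrink the lean and could remove it, although failures would then be dropped in every arm.
- **A reader might infer that the per-protocol analysis is worthless or the trial result biased.** Success rests on the FAS. The two sensitivity analyses in SAP 5.3.4 do not depend on per-protocol membership. SAP 2.4.1.2 requires a summary of exclusions and SAP 4.6 a listing of prohibited-treatment failures, so any effect would be visible.

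These points limit the size and reach of the concern. They do not close the gap. The exception sets out to keep failures, and it misses one kind of failure that the SAP itself defines.

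**Conclusion.** The point holds in a limited form. SAP 2.4.1.2 is not aligned with protocol 6.5.5 and 7.1, or with SAP 5.2.3.1 and 5.2.3.2, and these sections need to be reconciled. Only one pathway is affected: a guselkumab participant stopped for prohibited HS therapy before completing the Week 12 dose, with that as the recorded reason. Starts after the Week 12 dose are not affected.

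Where the pathway occurs, the guselkumab per-protocol rate rises and placebo does not. The increase is 0.9 points for one participant and 6.1 points for six, under the design rates and an assumed k. Zero or one is plausible, because the participant must both start therapy early and be coded outside the retained reasons. The direction follows from the text; the size cannot be fixed from it. The consequence is confined to the supportive per-protocol HiSCR analysis.

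**What to change.** In SAP 2.4.1.2, replace the second branch of the exception ("participants who started prohibited medications and continued receiving study agents prior to the specified timepoint for the endpoints will be included") so that the group retained reads: *participants who met the prohibited-medication/therapy treatment failure criterion (Section 5.2.3.1) before Week 16, whether or not study agent was then discontinued*. Keep them as treatment failures in all arms. The analgesic item in 5.2.3.1 points to 5.2.3.2.1, and SAP 4.6 ties it to the pain endpoints. The edit should leave it there and not turn analgesic use into a HiSCR failure.

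Make the change before the Week 16 lock and unblinding, so that the choice cannot be influenced by results. It costs one SAP sentence and needs no new data. The downside is that the per-protocol guselkumab rate may be slightly less favourable. No change to the clinical stopping rule is proposed.

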6.5.6. Concomitant Corticosteroid use for Conditions Other than HS

The use of systemic corticosteroids for indications other than HS should be limited to situations for which, in the opinion of the treating physician, there are no adequate alternatives. They should be used on a short-term basis, preferably for ≤2 weeks. Longer-term use of corticosteroids should be discussed with the medical monitor or designee and may require discontinuation of study drug. Inhaled, otic, ocular, nasal or other routes of mucosal delivery of corticosteroids are allowed throughout the study.

6.6. Dose Modification

No treatment/dose adjustment will be permitted through the study

6.7. Intervention After the End of the Study

No LTE is provided in this Phase 2 POC study. Participants and investigators will be informed that study intervention will not be made available to them beyond this protocol and that they should return to their treating physician for guidance.

7. DISCONTINUATION OF STUDY INTERVENTION AND PARTICIPANT DISCONTINUATION/WITHDRAWAL

A participant will be considered to have completed the study if he or she has completed assessments through Week 48 as specified in the Schedule of Activities (Section 1.3).

7.1. Discontinuation of Study Intervention

A participant's study intervention must be discontinued if any of the following occur:

- The investigator believes that for safety reasons or tolerability reasons (eg, AE) it is in the best interest of the participant to discontinue study intervention.
- The participant has a serious adverse reaction that is temporally related to an injection or an infusion including an injection-site or infusion reaction, resulting in bronchospasm with wheezing and/or dyspnea that requires ventilatory support OR that results in symptomatic hypotension with a decrease in systolic blood pressure >40 mm Hg or blood pressure <90/60 mm Hg. This may include events of National Cancer Institute Common Terminology Criteria for Adverse Events (NCI-CTCAE) toxicity grade ≥3. In general, discontinuation of study intervention administration must be considered for participants who develop a severe injection-site or infusion reaction.
- The participant or their legally acceptable representative withdraws consent/assent for administration of study intervention.
- The participant becomes pregnant or plans a pregnancy during the study period. Refer to Appendix 7 (Section 10.7), Contraceptive and Barrier Guidance and Collection of Pregnancy Information.
- The initiation of protocol-prohibited medications, treatments, or interventions (outlined in Section 6.5, Concomitant Therapy) that have an impact on HS efficacy evaluations.
- The participant has a malignancy including squamous cell skin cancer. Consideration may be given to allow participants, who develop ≤2 basal cell skin cancers and who are adequately treated with no evidence of residual disease, to continue to receive study intervention.
- A systemic opportunistic infection.
- A recurrent or chronic serious infection.
- The participant is deemed ineligible according to the following TB screening criteria:
 - A diagnosis of active TB is made.
 - A participant has symptoms suggestive of active TB based on follow-up assessment questions and/or physical examination or has had recent close contact with a person with active TB and cannot or will not undergo additional evaluation.

- A participant undergoing evaluation has a chest radiograph with evidence of current active TB and/or a positive QuantiFERON®-TB test result and/or 2 indeterminate QuantiFERON®-TB test results on repeat testing (refer to Section 8.2.11, Tuberculosis Evaluations) (and/or a positive tuberculin skin test result in countries in which the QuantiFERON®-TB test is not approved/registered or the tuberculin skin test is mandated by local health authorities).
- A participant receiving treatment for latent TB discontinues this treatment prematurely or is noncompliant with the therapy.
- The participant is unable to adhere to the study visit schedule or comply with protocol requirements.
- The participant has a reaction resulting in myalgia and/or arthralgia with fever and/or rash (suggestive of serum sickness and not representative of signs and symptoms of other recognized clinical syndromes) occurring 1 to 14 days after an injection of study intervention. These may be accompanied by other events including pruritus, facial, hand, or lip edema, dysphagia, urticaria, sore throat, and/or headache.
- The participant has his/her treatment assignment unblinded by the investigator.
- Sponsor decision.

Discontinuation of a participant's study intervention should be considered for:

• Participants with any type of suicidal ideation or behavior, or any self-injurious behavior, who are deemed to be at risk by the investigator. Discussion of such participants with the medical monitor or designee is required. For participants who report Suicidal Ideation with Intention to Act ("Ideation level 4"), suicidal ideation with specific plan and intent ("Ideation level 5"), suicidal behavior (actual suicide attempt, interrupted suicide attempt, aborted suicide attempt, or preparatory behaviors for making a suicide attempt) or any self-injurious behavior on a post-baseline C-SSRS assessment, the investigator risk assessment must be based upon evaluation by a mental health professional (see Section 8.2.5).

Participants who decide to discontinue study intervention administration for reasons other than those outlined above must be interviewed by the investigator to determine if a specific reason for discontinuing study intervention can be identified. Participants should be explicitly asked about the possible contribution of AEs to their decision to discontinue study intervention; investigators should confirm that any AE information elicited has been documented. If a participant elects to discontinue study intervention due to an AE, the event should be recorded as the reason for study intervention discontinuation, even if the investigator's assessment is that the AE would not require study intervention discontinuation. The reason for study intervention discontinuation must be documented in the eCRF and in source documents. Study intervention assigned to a participant who discontinues may not be assigned to another participant.

A participant will not be automatically withdrawn from the study if he or she must discontinue treatment before the end of the treatment regimen. Participants who discontinue study intervention but do not terminate study participation will continue to return for protocol-specified procedures and evaluations for approximately 12 weeks following the last dose of study intervention. The procedures and evaluations listed for the Early Termination Visit should also be performed approximately 12 weeks after the last dose of study intervention.

All procedures and evaluations must be conducted prior to a participant's withdrawal of consent.

